8.6.1 Response in Measurable Lesions

At baseline, the sum of the longest diameters (SumD) of all target lesions (up to 2 lesions per organ, up to total 5 lesions) is measured. At each subsequent tumor assessment (TA), the SumD of the target lesions and of new, measurable lesions (\geq 10 mm [lymph nodes \geq 15 mm in shortest diameter]; up to 2 new lesions per organ, total 5 new lesions) are added together to provide the total measurable tumor burden (TMTB):

TMTB = SumD target lesions + SumD new, measurable lesions.

Percentage changes in TMTB per assessment time-point describe the size and growth kinetics of both old and new, measurable lesions as they appear. At each TA, the response in target and new, measurable lesions is defined based on the change in TMTB (after ruling out irPD) as follows:

Complete Response (irCR)	Complete disappearance of all target and new, measurable lesions, with the exceptions of lymph nodes which must decrease to $<$ 10 mm in short axis.
Partial Response (irPR)	Decrease in TMTB \geq 30% relative to baseline.
Stable Disease (irSD)	Not meeting criteria for irCR or irPR, in absence of irPD.
Progressive Disease (irPD)	Increase in TMTB \geq 20% relative to nadir.

8.6.2 Response in Non-measurable Lesions

At each TA, the presence of any new, non-measurable lesions is assessed. The presence of such lesions will rule out an overall response of irCR. An increase in the size or number of new, non-measurable lesions does not necessarily imply an overall response of irPD; if these lesions

become measurable (≥ 10 mm) at a subsequent TA, their measurement will at that point start to contribute to the TMTB. In addition, the response in non-target lesions is defined as follows:

Complete Response (irCR)	Complete disappearance of all non-target lesions.
Stable Disease (irSD)	Non-target lesions are stable.
Progressive Disease (irPD)	Unequivocal increases in number or size of non-target lesions. To achieve unequivocal progression of non-target lesions, there must be an overall level of substantial worsening of non-target disease that is of a magnitude that the treating physician would feel it is important to change therapy.*

*NOTE: Equivocal findings of progression of non-target lesions (e.g., small and uncertain new lesions; cystic changes or necrosis in existing lesions) should be considered irSD, and treatment may continue until the next scheduled assessment.

8.6.3 Evaluation of Biomarkers

Serum CA-125 must be within normal limits for a subject to be considered in complete clinical response.

8.6.4 Overall Response

The OR according to the irRECIST is derived from the responses in measurable lesions (based on TMTB) as well as the presence of any non-measurable lesions as follows:

Complete Response (irCR)	Complete disappearance of all lesions (whether measurable or not); lymph nodes must decrease to < 10 mm in shortest dimension. Serum CA-125 within normal limits.
Partial Response (irPR)	Decrease in TMTB $\geq 30\%$ relative to baseline.
Stable Disease (irSD)	Not meeting criteria for irCR or irPR, in absence of irPD.
Progressive Disease (irPD)	Increase in TMTB $\geq 20\%$ relative to nadir.

Target Lesions Baseline (Index) and New Measurable Lesions	Non-Target Lesions*		irRECIST Overall Response
	Baseline Lesions	Unequivocal New Lesions	
Total Measurable Tumor Burden (TMTB)			
irCR	irCR	No	irCR
irCR	irSD	No	irPR
irPR	irCR or irSD	No	irPR
irSD	irCR or irSD	No	irSD
irPD	Any	Yes or No	irPD
Any	Unequivocal Progression	Yes or No	irPD
Any	Any	Yes	irPD

*Any increase in the size or number of non-measurable lesions does not necessarily imply an overall response of irPD. If new, non-measurable lesions become measurable (≥ 10 mm) at a subsequent TA, their measurement will at that point start to contribute to the TMTB. To achieve unequivocal progression of non-target lesions, there must be an overall level of substantial worsening in non-target disease that is of a magnitude that the treating physician would feel it is important to change therapy. Equivocal findings of progression of non-target lesions (e.g., small and uncertain

CONFIDENTIAL

new lesions; cystic changes or necrosis in existing lesions) should be considered irSD, and treatment may continue until the next scheduled assessment.

8.6.5 Duration of Response

Duration of overall response: The duration of overall response is measured from the time measurement criteria are met for irCR or irPR (whichever is first recorded) until the first date that progressive disease (irPD) is objectively documented (taking as reference for progressive disease the smallest measurements recorded [nadir] since the treatment started).

The duration of overall irCR is measured from the time measurement criteria are first met for irCR until the first date that irPD is objectively documented.

Duration of stable disease: Stable disease is measured from the start of the treatment until the criteria for irPD are met.

8.7 Exploratory Assessment of Correlative Immunologic Research

Please refer to the lab manual for additional instructions and information on lab specimen handling and logistics.

8.7.1 Phenotypic Analysis of PBMCs

Samples for peripheral blood T-cells will be collected at the time points designated in the flowchart (Section 3.2). Peripheral blood cell subsets will be quantitated through multiparametric flow cytometry for the following T-cell subsets: CD3, CD4, CD8, FoxP3. T-cell subsets will be assessed for activation/exhaustion by expression of PD-L1, Ki-67, ICOS, PD-1, LAG-3, TIM-3, CTLA-4. PBMC may additionally be evaluated in a T-regulatory cell panel for the following: CD3, CD4, CD8, FoxP3, CD25, CD127, CD45A, CCR7, GITR, OX40, Ki-67, PD-1, CD56.

8.7.2 Myeloid Derived Suppressor Cells (MDSC)

MDSCs constitute a heterogeneous population of immature myeloid cells with various immune suppressive functions including suppression of T-cell proliferation, inducement of T-cell apoptosis and disruption of T-cell signaling pathways. Levels of circulating MDSCs are increasingly recognized as important in determining clinical responses to novel drugs for cancer and autoimmune disease. Samples will be collected for analyses at time points designated in the study flowchart (Section 3.2).

MDSCs are defined as events that are:

Lineage^{neg}, CD14^{pos}, HLA--DR^{low/neg}

Each sample is analyzed using well-established flow cytometry techniques for the presence of MDSCs. For each sample a single data point will be delivered, being the mean of values for the percentage of Lineage^{neg}, CD14^{pos} events that are HLA--DR^{low/neg} to study the effects of treatment on levels of MDSCs.

8.7.3 Quantification of Tumor-specific T-cell Responses

PBMCs will be collected at the time points designated in the flowchart (Section 3.2). Peripheral blood T-cell responses against known tumor-associated antigens (TAAs) expressed in most ovarian cancers, including Her-2, p53, MUC-1, hTERT, survivin, mesothelin, folate binding protein, MAGE-A3, NY-ESO-1, SP-17, and WT1 will be assessed. Overlapping peptides (15-mers overlapping by 11 amino acids) that allow assaying T-cells independently of the haplotypes will be used. Functional assays will be performed both *ex vivo* and after *in vitro* T-cell expansion and readouts will include the analysis of biomarkers in the culture supernatant (e.g. using MSD to screen for up to 40 analytes as IFN- γ and granzyme-B, for instance), IFN- γ ELISpot and polychromatic intracellular cytokines staining. As controls, T-cell response to control non-tumor related peptides (e.g. the standard CEF peptide pool including immunodominant peptides from Cytomegalovirus, Epstein Barr Virus and Influenza or tetanus toxoid) will be tested.

Whether therapy elicits T-cells specific against private mutated tumor antigens will be tested. Candidate antigens will be identified through exome sequencing of tumor tissue combined with gene expression profiling, and will be screened for candidate peptides for the subject's haplotypes using appropriate bioinformatics algorithms, tested and validated in the Lausanne

CONFIDENTIAL

Ludwig center. *In silico*-predicted candidate peptides will be tested for fitness and binding affinity to cognate class I HLAs using recombinant HLA in an *in vitro* screening algorithm developed by [name] at Ludwig Lausanne and provided by TC Metrics. Finally, best-in-class peptides will be validated using PBMCs as above.

8.7.4 Baseline Immune Responsiveness to TLR8 activation

TruCulture™ samples will be collected at the time points designated in the flowchart (Section 3.2). Processed TruCulture™ tubes will be analyzed by Myriad/Rules Based Medicine (Austin, TX) to assess baseline immune responsiveness motolimod and MEDI4736.

Considerable variability in immune reactivity can exist between individuals. Despite the fact that motolimod activates a specific receptor (TLR8) on a restricted class of dendritic cells and monocytes, marked differences in responsiveness to treatment with this agent may relate to pre-existing difference in immune activation at baseline. It is hypothesized that measurable differences in response to motolimod at baseline (prior to dosing) may predict the pharmacodynamic response, and potentially clinical responses, to this agent.

A validated assay (TruCulture™) will be used to measure the baseline response to motolimod. In preliminary studies using healthy volunteers and cancer patients and the TruCulture system, VentiRx has demonstrated variability between individuals following immune activation with lipopolysaccharide or motolimod, particularly with regards to IFN- γ and interleukin-12 production. Data from TruCulture at baseline will be correlated with TLR8 SNP data, immune responses after treatment, and clinical responses.

NOTE: PER Amendment 2, samples will no longer be collected for analysis of TruCulture™, as the analyses were related to motolimod dosing. The collection time points for these assays have been removed from the flowchart in Section 3.2.

8.7.5 Immune Landscape: TILs and Tumor Microenvironment

Immunohistochemistry (IHC): Unstained sections of tumor will be analyzed by The Center of Experimental Therapeutics in Lausanne, Switzerland, where an immune signature will be assessed using a multiplexed immunohistochemical approach followed by multispectral imaging and unmixing. Multispectral imaging and linear unmixing offers the ability to analyze in a comprehensive, spatially oriented and quantitative fashion tumor slides, each stained with multiple antibodies, in either a brightfield (up to 3-4 antibodies + counterstain) or fluorescence (up to 6-8 antibodies + counterstain + autofluorescence removal) mode. More specifically, lineage specific markers i.e. CD3, CD4, CD8 for T lymphocytes (and FoxP3 for Tregs), combined with markers of activation, or functional exhaustion, for example CD45RO, CD38, HLA-DR, TIA-1, granzyme-B, Ki67, PD-1, ICOS, LAG-3, Tim-3 and/or CTLA-4 will be used. Furthermore, the spatial distribution of immune cell subsets with the level of expression on tumor cells of major components of the antigen presenting machinery i.e. HLA class I and II molecules, β 2 microglobulin, tapasin, and TAP1 and 2 will be evaluated. Tumor cells and the whole microenvironment can also be interrogated for immunosuppressive factors such expression of PD-L1 and PD-L2, TGF-b, IL-10, COX1 and 2, IDO-1 etc. Tumor cells can be interrogated for proliferation (Ki67), apoptosis (cleaved caspase-3), necrosis (HMGB1) or autophagy (beclin, LC3). Finally, innate cells can be characterized, for example by CD68 and CD163 for M1 and M2

CONFIDENTIAL

macrophages, CD33 for MDSCs and NKp46 for NK cells. Finally, the vasculature will be interrogated using several markers of activated and tumor endothelium and pericytes.

As a complementary approach to the IHC, Nanostring platform will be used to assess the mRNA expression level of genes reflecting tumor microenvironment signatures, including genes of innate and adaptive immunity, inflammation, wound healing and angiogenesis.

8.7.6 TCR sequencing

In order to better understand the role of TCR in the control of tumor, next generation sequencing will be used to perform a large and comprehensive analysis of the repertoire in various tumors for whose clinical outcome is known. DNA will be extracted from tumors and PBMCs to sequence the TCR beta chain of the infiltrating lymphocytes. The data will reveal the nucleotide sequences of the TCR present and thus allow analysis of the diversity and the clonality of the repertoire. PBMCs will be assayed from 3 time points, which will be matched as closely as possible to the tumor biopsies (baseline, Cycle 2 Day 1 and the PBMC collection closest to disease progression).

8.7.7 Immune biomarkers

Cytokines and chemokines in peripheral blood will be assessed using the Rules Based Medicine platform (HumanMAP®). HumanMAP® samples will be collected at the time points designated in the flowchart (Section 3.2). Samples will be analyzed by Myriad/Rules Based Medicine (Austin, TX), and plasma will be used to assess specific analytes including chemokines, cytokines, and other inflammatory mediators by protein array technology.

Plasma obtained from subjects pre- and post-treatment will be screened by ELISA for the presence of antibodies against a panel of cancer testis antigens and other tumor-associated antigens.

NOTE: PER Amendment 2, samples will no longer be collected for analysis of HumanMap®. The collection time points for these assays have been removed from the flowchart in Section 3.2.

8.7.8 Pharmacogenomics

DNA will be analyzed by the University of Washington, Tumor Vaccine Group (Seattle, WA) and used to examine single nucleotide polymorphisms (SNPs) in the TLR8 gene by conventional methods. An aliquot of the PBMC collection and/or tumor biopsy/archival tissue will be used for pharmacogenomics.

Genes encoding TLRs, particularly those encoding the intracellular TLR (TLR3, TLR7, TLR8 and TLR9) are evolutionarily conserved. Still, various single nucleotide polymorphisms (SNPs) in the TLR8 gene have been identified from large scale sequencing efforts in multiple ethnic populations. Recently, a common TLR8 SNP [denoted TLR8 A1G (rs3764880)] has been found to be associated with various infectious diseases, notably progression of HIV and TB. This allele is present in all populations tested, and is found at a frequency of approximately 30% in most ethnic groups. While one report suggests that the TLR8 A1G encodes a variant of TLR8 which decreases activity relative to the wild type allele, there are scant data, at present, to support this conclusion.

Given the relatively high allele frequency of this common TLR8 genetic variant, the potential functional differences in this allele, and the human genetic association between this variant and several infectious diseases, it is reasonable to genotype individuals from clinical trials investigating motolimod. Reliable methods to analyze DNA from blood or saliva to detect the TLR A1G SNP have been developed. Genotyping of all subjects in the proposed trial for the A1G SNP will be conducted to assess the potential relevance of this allele to clinical responses (related to efficacy and safety) following treatment with motolimod.

8.7.9 BRCA status of tumors

The BRCA status of tumors by testing for mutations in the full *BRCA1* and *BRCA2* exons as well as additional genes involved in the homologous recombination repair pathway will be assessed. Expression of BRCA1 and BRCA2 proteins in tumors by immunohistochemistry will be tested; absence will indicate loss of expression, presumably through epigenetic regulation.

8.7.10 MEDI4736 PK and Immunogenicity for Anti-drug Antibodies (ADA)

A validated electrochemiluminescence assay (ECLA) using a Meso Scale Discovery (MSD) platform will be used for the quantitative determination of MEDI4736 concentrations in serum. Anti-MEDI4736 antibodies in human serum will be detected using a validated MSD electrochemiluminescence assay.

NOTE: PER Amendment 2, samples will no longer be collected for analysis of MEDI4736 PK and immunogenicity for anti-drug antibodies (ADA), as sufficient samples have already been collected. The collection time points for these assays have been removed from the flowchart in Section 3.2.

8.7.11 sPD-L1

The association of sPD-L1 with response to treatment and clinical outcome will be evaluated.

NOTE: PER Amendment 2, samples will no longer be collected for analysis of sPD-L1, as sufficient samples have already been collected. The collection time points for these assays have been removed from the flowchart in Section 3.2.

8.7.12 Circulating soluble factors

Analyses of circulating levels of soluble factors such as cytokines and chemokines may include but are not limited to VEGF, FGF, TGF, IL-1 IL-2, IL-4, IL-6, IL-8, IL-10, IFN, G-CSF, TNF. Their association with treatment and clinical outcome will be explored.

NOTE: PER Amendment 2, samples will no longer be collected for analysis of circulating soluble factors, as sufficient samples have already been collected. The collection time points for these assays have been removed from the flowchart in Section 3.2.

8.7.13 Additional translational and exploratory studies

Optional research studies may only be performed for subjects who voluntarily gave their consent for additional correlative research on the informed consent document. Subjects who declined consent to participate in additional translational studies will have their samples destroyed at the end of the study. Refusal to participate in this optional research will involve no penalty or loss of

benefits to which the subject would otherwise be entitled. Based on the data generated during the study and/or in other studies, not all samples from subjects consenting to this optional research may be utilized.

8.7.14 mRNA/miRNA Profiling

Whole blood samples (pre- and during MEDI4736 treatment) will be collected and preserved in PAXgene tubes to prepare miRNA/mRNA samples for future analyses of transcript and/or miRNA expression mRNA levels of selected inflammatory/immune and cytokine pathways which may include but are not limited to IL-6, IL-8, TIMP1, FCRG2B, LIF, IFN, LARGE, CXCL10, SOCS3 may be measured, as well as their association with MEDI-4736 treatment outcome. RNA analyses may be conducted to generate hypotheses associated with the mechanisms of action of immunotherapy and/or to identify subsets of subjects responsive to MEDI4736.

8.8 ECOG Performance Status

ECOG Performance Status: Developed by the Eastern Cooperative Oncology Group, [name], Group Chair. *

GRADE	ECOG PERFORMANCE STATUS
0	Fully active, able to carry on all pre-disease performance without restriction
1	Restricted in physically strenuous activity but ambulatory and able to carry out work of a light or sedentary nature, e.g., light house work, office work
2	Ambulatory and capable of all selfcare but unable to carry out any work activities; up and about more than 50% of waking hours
3	Capable of only limited selfcare; confined to bed or chair more than 50% of waking hours
4	Completely disabled; cannot carry on any selfcare; totally confined to bed or chair
5	Dead

CONFIDENTIAL

8.9 Details for Subjects Who Continue Optional MEDI4736 Treatment beyond the Core Study

According to Section 3.1.12, optional MEDI4736 treatment extension beyond the Core Study is available for subjects who complete the Core Study with Stable Disease or better. The optional treatment extension will be permitted upon agreement with the subject, Sponsor and Investigator, and it may continue until confirmed disease progression, unless there is unacceptable toxicity, withdrawal of consent, or another discontinuation criterion is met.

Subjects who receive optional study treatment extension will receive the currently recommended fixed dose of 1500 mg MEDI4736 Q4W for subjects > 30 kg. If a subject's body weight drops to ≤ 30 kg, the subject will receive weight-based dosing equivalent to 20 mg/kg Q4W for MEDI4736 as long as the body weight remains ≤ 30 kg (e.g., a 30 kg subject would receive a 600 mg dose; a 25 kg subject would receive a 500 mg dose; etc.). When the weight improves to >30 kg, the subject may return to fixed dosing of MEDI4736 1500 mg.

The following procedures will be implemented for subjects who receive optional study treatment:

1. Fixed dose of 1500 mg MEDI4736 will be used; preparation details are provided in Section 6.3.3.2.
2. Administration of MEDI4736 will proceed according to Section 6.3.4.
3. Subjects will be monitored by assessment of vital signs before, during and after each MEDI4736 dose administration according to Section 6.3.5.
4. The first MEDI4736 dose during optional treatment extension will be administered as follows:
 - a. Last dose in Core Study + 2 weeks (± 3 days) for subjects on Q2W regimen in Core Study, OR
 - b. Last dose in Core Study + 4 weeks (± 3 days) for subjects on Q4W regimen in Core Study
5. After the first dose, MEDI4736 dosing will continue Q4W.
6. The flowchart for optional treatment extension, which is provided in Section 8.9.1, will be followed.
7. AE/SAE collection and reporting will be performed according to the protocol requirements (Section 7.1) and until disease progression is documented. For AEs/SAEs that may be ongoing at the time of disease progression, follow-up will be performed until resolution or stabilization of the events or up to 90 days after the last dose of MEDI4736.

8.9.1 Study Flowchart for Subjects Who Continue Optional MEDI4736 Treatment beyond the Core Study

Study Flowchart for Subjects who Continue Optional MEDI4736 Treatment after Core Study	Optional Study Treatment ^{1,2} (Q4W following first optional study treatment dose)	On Study Follow-up			Post Study Follow-Up
		Last Study Drug Administration +28 ±3 days	Last Study Drug Administration +56 ±7 days	Last Study Drug Administration +90 ±7 days End of Study	
Study Drug					
MEDI4736 (IV)	1500 mg				Every 3 months for 3 years from initiation of treatment. Clinical outcomes data (dates of progression/relapse and survival) will be recorded (See Section 3.1.16).
Tumor & Disease Assessments					
Disease Assessment by RECIST and irRECIST (including appropriate imaging)	SOC	+84 ± 7 days from last disease assessment			
Study Procedures & Examinations					
Physical Exam (incl. weight and ECOG Perf Status)	X	X	X	X	
Vital Signs (T, HR, BP, RR) ⁴	X	X	X	X	
12-Lead ECG ³	At first optional treatment visit, then Q12W	X			
Echocardiogram or MUGA	At first optional treatment visit, then Q12W	X			
Concomitant Medication / Procedure (name, indication, dose, route, start & end dates)	X	X	X	X	
Adverse Events (starting or worsening after IC) ⁵	X	X	X	X	
Specimens for Laboratory Procedures					
Blood Hematology (complete blood count, differential, platelets) ³	At first optional treatment visit, then Q12W	X		X	
Chemistry (gluc., BUN, crea., Na, K, Ca, Cl, CO ₂ , PO ₄ , Mg, prot., alb., Tbili., AST, ALT, ALP, LDH) ³	At first optional treatment visit, then Q12W	X		X	
Chemistry cont. (Amylase and lipase) ³	At first optional treatment visit, then Q12W	X		X	
Chemistry cont. (Free T ₃ , Free T ₄ , TSH) ³	At first optional treatment visit, then Q12W	X		X	
Serum pregnancy test ³	At first optional treatment visit, then Q12W	X		X	
CA-125 ³	SOC	+84 ± 7 days from last disease assessment			
Specimens for Correlative Assessments					
PBMC/Plasma Collection & Banking ³	At first optional treatment visit only	X		X	
MDSC (Seramatrix) ³ (US sites only)	At first optional treatment visit only	X			
Tumor Biopsy (Tumor microenvironment, PD-L1 expression, TCR sequencing)		optional at disease progression			
Pharmacogenomics (including BRCA1 and BRCA2 tumor status) ⁶					
PAX RNA ³		optional at disease progression			
Q2W = every 2 weeks; Q4W = every 4 weeks; Q8W = every 8 weeks; Q12W = every 12 weeks; SOC = Standard of Care					
1 - First MEDI4736 dose during optional treatment extension will be administered according to the following schedule:					
a) Last dose in Core Study + 2 weeks (± 3 days) for subjects on Q2W regimen in Core Study OR					
b) Last dose in Core Study + 4 weeks (± 3 days) for subjects on Q4W regimen in Core Study					
2 - After first dose, MEDI4736 dosing will continue Q4W according to Section 8.9; assessments will continue Q4W unless otherwise noted.					
3 - Collected pre-dose. Note: It is strongly recommended that results for hematology, chemistry and pregnancy test (when applicable) are reviewed before dosing. Pregnancy tests are not required for subjects who are not of child-bearing potential as defined in Section 5.2, #17					
4 - See Section 6.3.5 for assessment of vital signs before, during and after administration of MEDI4736 dose.					
5 - See section 7.1.5 for details regarding collection of AEs for 90 days after last study drug administration.					
6 - An aliquot of the PBMC and/or Tumor Biopsy tissue will be used for pharmacogenomics – a separate sampling is not needed					

CONFIDENTIAL

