3.1.12 Optional Study Treatment Extension

Optional MEDI4736 treatment extension beyond the initial 12-cycle treatment period (Core Study) will be available for subjects who complete the Core Study with Stable Disease or better. The optional treatment extension will be permitted upon agreement with subject, Sponsor and Investigator, and it may continue until confirmed disease progression, unless there is unacceptable toxicity, withdrawal of consent, or another discontinuation criterion is met. See

Section 8.9 for details regarding treatment extension and collection / reporting of adverse events during this period.

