7.1.5 General Reporting Requirements

All serious and non-serious adverse events must be documented in the source records and on the respective section of the CRF, regardless of severity or the assumption of a causal relationship. The documentation includes: dates of onset and resolution, severity, seriousness, study drug intervention, treatment and outcome, as well as the causal relationship between the event and

CONFIDENTIAL

the study drug in accordance with Section 7.1.4. This documentation is required for all AEs that occur:

- a. from the date of signing the informed consent, and
- b. until the off-study date or 90 days after the last administration of study drug, whichever is longer, or until a new treatment is initiated (See Section 3.1.10 for subjects who begin other anti-cancer treatment).

Immune Related Adverse Events (irAEs) will be collected from the time of informed consent through 90 days after the last dose of the last study treatment (regardless of initiation of another therapy).

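### Section 8.9 item 7 ends extension AE/SAE collection at documented progression, in conflict with the 90-day window in Section 7.1.5 and the 8.9.1 flowchart

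*Protocol*

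**What the plan says.** Protocol Section 8.9 lists the procedures for the optional extension. Item 7 states: "AE/SAE collection and reporting will be performed according to the protocol requirements (Section 7.1) and until disease progression is documented". Its next sentence deals with the time after progression and names only events already open: "For AEs/SAEs that may be ongoing at the time of disease progression, follow-up will be performed until resolution or stabilization of the events". The same sentence gives day 90 from the final MEDI4736 dose as the alternative limit. New-onset events after progression are not mentioned.

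Other parts of the Protocol set a different window:

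- Section 7.1.5 requires documentation of all AEs "until the off-study date or 90 days after the last administration of study drug, whichever is longer, or until a new treatment is initiated". Progression is not an end point there.
- Section 7.1.5 collects immune-related AEs (irAEs) "through 90 days after the last dose of the last study treatment (regardless of initiation of another therapy").
- The Section 8.9.1 flowchart has a row "Adverse Events (starting or worsening after IC") that is marked at the treatment visits and at +28, +56 and +90 days after the last dose. Footnote 5 to that row reads: "See section 7.1.5 for details regarding collection of AEs for 90 days after last study drug administration".
- Section 8.9 item 6 says that this flowchart applies.

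On the length of extension treatment, Section 3.1.12 says that "it may continue until confirmed disease progression". The Synopsis and Section 3.1.12 both refer the reader to Section 8.9 for AE collection and reporting during the extension.

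**The concern.** Two end points are given for the same data. Item 7 is the specific rule, and it is the text to which the Synopsis and Section 3.1.12 direct sites. A site that follows it could stop recording new AEs and SAEs on the day progression is documented. Section 7.1.5 and the flowchart would have the site continue to 90 days after the last dose.

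The choice of word adds a second problem. Item 7 turns on *documented* progression, while treatment may run to *confirmed* progression. If the two dates differ, new events in a subject who is still being dosed fall outside item 7.

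At stake is the completeness of safety data in the subjects with the longest MEDI4736 exposure, since they have already completed 12 cycles. Section 7.1.4 itself warns that immune-therapeutic agents can have very late effects.

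**Working it through.** The main check is a comparison of passages. Arithmetic enters only for the scale.

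**1. The rules side by side**

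| Source (Protocol) | End of collection for new AEs | After progression |
|---|---|---|
| 8.9 item 7 | As in Section 7.1, and to documented progression | Ongoing events only |
| 7.1.5, all AEs | Off-study date or 90 days after last dose, the later of the two, or new treatment | No separate rule |
| 7.1.5, irAEs | 90 days after last dose, whatever therapy follows | No separate rule |
| 8.9.1 flowchart, footnote 5 | Visits at +28, +56, +90 days; refers to 7.1.5 | No separate rule |

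**2. Can item 7 be read in line with 7.1.5?** Its first sentence invokes Section 7.1, so *and until* could mean *and at least until*. The second sentence works against this. If new events were still collected to day 90, a provision limited to ongoing events would be unnecessary. Read together, the two sentences make progression the cut-off for new events. The text is at best ambiguous.

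**3. Documented and confirmed progression.** Section 3.1.10.1 allows therapy after RECIST 1.1 progression until confirmation, under conditions. A gap between the two dates, with dosing in it, is therefore possible.

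**4. Does the SAP settle it?** No. SAP Section 3.3.2 defines a treatment-emergent AE by onset or worsening after the first dose and sets no upper limit. The AE tables will contain whatever the sites recorded.

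**5. Number of subjects.** Inputs from Protocol Section 6.4: 15% of subjects continue for 12 cycles; 53 subjects; 3 vials per cycle at 1500 mg; 20% overage. The overage is stated for the core supply and is assumed here for the extension.

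- Subjects: 0.15 × 53 = 7.95, about 8.
- Vials: 7.95 × 12 × 3 × 1.2 = 343.4. The plan states 343, so its figure is reproduced.
- With 41 subjects instead: 0.15 × 41 = 6.15, and 6.15 × 12 × 3 × 1.2 = 265.7, which does not match. The 15% therefore applies to 53 subjects.

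**6. Days at stake per affected subject, if item 7 is applied as a hard stop.** The timings are assumptions; the documents do not give them.

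- Progression documented g days after the last dose, no further dose: 90 − g. For g = 0, 14 and 28 this gives 90, 76 and 62 days.
- Last dose k days after documented progression: k + 90. For k = 28 and 56 this gives 118 and 146 days, of which 28 and 56 are on treatment.
- If Section 7.1.5 and the flowchart govern: 0 days.

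For AEs other than irAEs these are upper limits, because Section 7.1.5 itself ends collection when a new treatment starts.

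**The case against.** The strongest reply is that the 90-day rule already stands inside the extension section. Item 7 invokes Section 7.1, item 6 requires the flowchart, the flowchart marks AEs to +90 days, and footnote 5 cites Section 7.1.5. Data are lost only if a site applies one half of item 7 and passes over the rest. This stands as a reason to speak of a risk. It does not remove the conflict, because item 7 is the text to which sites are sent.

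A reader might go further and infer that extension safety data are incomplete by rule, that late irAEs go unrecorded, and that every extension subject is affected. The documents do not support these inferences:

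- **irAEs.** Section 7.1.5 covers them for 90 days after the last dose regardless of new therapy. Section 3.1.16 adds a post-study query about irAEs in the same 90 days. The query does not reach other new AEs or SAEs, so the protection is partial.
- **Every subject.** Extension treatment can also end for toxicity, withdrawn consent or another criterion. A subject who stops for such a reason loses nothing under item 7 unless progression is then documented within the 90 days. If it is not, item 7 could even be read to run past day 90. The documents give no figure for how often progression is the reason for stopping.
- **Gap before confirmation.** Section 8.6 asks for repeat imaging when irPD is found at or before 12 weeks from the start of treatment. Extension subjects have completed 12 cycles of 28 days (336 days, or 48 weeks). Continuing under Section 3.1.10.1 requires consent, clinical criteria and the investigator's judgement. *Documented* in item 7 may also be meant as documentation of the confirmed event. The gap is possible for some subjects, not automatic.

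**Conclusion.** The point holds as an internal inconsistency that should be corrected. Section 8.9 item 7 gives an AE/SAE end point that conflicts with Section 7.1.5, the Section 8.9.1 flowchart and footnote 5, and it uses a different progression term from the treatment rule. A site applying item 7 could fail to record new-onset AEs and SAEs after documented progression, including during continued dosing. The loss is a possibility that depends on how sites read the text; it is not a certainty, and irAEs are the best protected part.

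The size is modest. About 8 subjects would enter the extension if the 15% supply assumption on 53 subjects is right, and essentially only those who stop for progression are exposed. The range of 62 to 146 days per affected subject rests on the assumed timings above and on item 7 being applied as a hard stop.

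**What to change.** In Section 8.9 item 7, delete the clause that runs collection to documented progression, and refer directly to the whole of the Section 7.1.5 window. That means all AEs and SAEs to the later of the off-study date and 90 days after the last dose, or to the start of a new treatment, and irAEs through 90 days after the last dose whatever therapy is started. Both parts are needed: a shortened version that drops the off-study date would create a new discrepancy. The provision for ongoing events can stay if it is worded so that it does not limit collection of new ones. Item 7, Section 7.1.5 and the flowchart would then agree.

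With progression removed from the AE rule, the difference between documented and confirmed progression no longer affects collection, and no treatment rule is changed. The cost is a small change to one item of the protocol and slightly more AE data entry at the +28, +56 and +90 day visits, which are already scheduled.
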